The protocol, informed consent form(s), recruitment materials, and all participant materials will be submitted to the Institutional Review Board (IRB) for review and approval. Approval of both the protocol and the consent form must be obtained before any participant is enrolled. Any amendment to the protocol will require review and approval by the IRB before the changes are implemented to the study. In addition, all changes to the consent form will be IRB-approved; a determination will be made regarding whether a new consent needs to be obtained from participants who provided consent, using a previously approved consent form.

[figure not shown]
1 PROTOCOL SUMMARY

1.1 SYNOPSIS

Title:	Postoperative Nudges to Reduce Opioid Prescribing (POST-OP)
Study Description:	This study tests the effectiveness of two email-based behavioral nudges, one based on peer behavior and one based on best practice guidelines, in reducing excessive opioid prescriptions after surgery. It will be conducted in three surgical specialties (general surgery, orthopedic surgery, and obstetric/gynecological surgery) at 19 hospitals within one healthcare system. At each hospital, these specialties will each be randomized to a control group or one of two nudge groups. Both types of email-based nudges are expected to reduce opioid prescribing after surgery.
Objectives:	Primary Objective: Health Services Research Secondary Objectives: Basic Science
Endpoints:	Primary Endpoint: Share of discharge opioid prescriptions above prescribing guidelines Secondary Endpoints: 
• Morphine milligram equivalents (MMEs) prescribed at discharge• Days' supply of opioids prescribed at discharge• Share of discharges where any opioid was prescribed• Share of patients on opioids for greater than 3 months post-discharge• Number of 30-day all-cause emergency department visits• Number of 30-day all-cause hospitalizations• Share of discharge opioid prescriptions above prescribing guidelines in the year after the intervention ends

Study Population:	Surgeons in northern California
Phase:	N/A
Description of Sites/Facilities Enrolling Participants:	19 Sutter Health hospitals
Description of Study Intervention:	Each month for one year, surgeons in the nudge groups will receive emails comparing their opioid prescribing either to their peers' prescribing or to prescribing guidelines.
Study Duration:	24 months
Participant Duration:	12 months

1.2 SCHEMA

1.3 SCHEDULE OF ACTIVITIES (SOA)

Nudges will be delivered on the third Tuesday of each month for 12 months, October 2021 through September 2022. Data will be collected continuously, with data from the first through last day of the previous calendar month informing whether a nudge is triggered and, if so, the content of the nudge.

After 12 months, the nudges will stop, but data will be collected continuously for another 12 months to assess the persistence of any effects of the nudges.

2 INTRODUCTION

2.1 STUDY RATIONALE

Physician opioid prescribing practices are a major upstream contributor to increases in chronic opioid use, opioid addiction and overdose deaths. Opioid prescribing after surgery is an important intervention target, as opioids are commonly overprescribed after surgery, post-operative opioid prescribing is a risk factor for chronic opioid use, and unused opioids prescribed for patients after surgery are an important reservoir of opioids available for misuse and diversion.

2.2 BACKGROUND

Despite high awareness of the opioid epidemic, clinicians still overprescribe opioids after surgery.¹⁻⁷ This post-operative overprescribing puts both patients and communities at risk, increasing the patient's likelihood of developing chronic opioid use⁸⁻¹⁴ or opioid-induced ventilatory impairment¹¹ and adding to the reservoir of unused opioids available for misuse and diversion.^{11, 15}

The discrepancy between clinicians' awareness of the opioid epidemic and the degree of overprescribing—over half of opioid pills prescribed after surgery go unused⁷—suggests that prescribing practices are not based on purely rational decisions. Indeed, behavioral research has shown that judgment and decision making of both laypeople and experts in a variety of disciplines falls short of rational standards in systematic and predictable ways.¹⁶⁻¹⁹ Even well-informed clinicians make cognitive errors when estimating the benefits and harms of treatment, and these errors are especially likely where there is uncertainty about risks and benefits (as with opioid prescribing decisions for individual patients).²⁰

In recent years, behavioral economists and experimental psychologists have successfully leveraged behavioral insights to design “choice architecture” that “nudges” individuals to make better decisions without infringing on their freedom of choice.^{21, 22} Such behavioral nudges are promising strategies for changing clinician prescribing behavior because they are often more cost-effective than traditional interventions,²³ can be integrated into existing clinical workflows, and are rapidly scalable once built.

One powerful type of behavioral nudge relies on the strong motivation that most people have to conform with their peers' behavior.^{24, 25} Abundant research has found that people (including clinicians) are strongly motivated to adhere to prevailing social norms,^{24, 25} and that nudges based on describing social norms can be used to influence prescribing decisions.²⁶

Another type of behavioral nudge relies on motivation to follow injunctive norms—to do what is considered the “right thing to do”. For example, clinicians may be motivated to follow best practice guidelines published by a well-respected organization. Previous studies suggest that such guidelines are in reality often ignored and thus ineffective in changing behavior,^{27, 28} but there is insufficient evidence to determine whether they are more or less effective than nudges that describe peer behavior.

Both of these types of nudges—nudges based on descriptive norms and nudges based on injunctive norms—have been applied to the issue of excessive post-operative opioid prescribing.²⁹⁻³⁸ The results have been promising, but because most of these studies have used a pre-post design, it is possible that the observed decreases in prescribing can be explained by a secular trend. Furthermore, all of these studies have bundled and tested different interventions together (e.g., grand rounds presentations or

patient education in addition to nudges), making the effectiveness of the nudges alone unclear. Accordingly, the evidence base for the effectiveness of behavioral nudges in influencing post-operative opioid prescribing is limited.

2.3 RISK/BENEFIT ASSESSMENT

2.3.1 KNOWN POTENTIAL RISKS

We believe that the risk presented by our nudge interventions is negligible, both because the nudges do not prevent the clinicians from using their own clinical judgment and because previous studies have found that reducing the amount of opioids prescribed after surgical operations did not affect patient satisfaction^{39, 40}, pain scores³⁹⁻⁴¹, or refill rates⁴²⁻⁴⁴.

2.3.2 KNOWN POTENTIAL BENEFITS

By simultaneously addressing both opioid overprescribing and the science of provider behavior change, we both improve health and advance science. From a public health perspective, overprescribing is the major upstream driver of increases in chronic opioid use and opioid misuse (including the transition to heroin), and studies similar to ours have been successful in curbing this overprescribing.²⁹⁻³⁸ From a scientific perspective, examining the comparative effectiveness of ways to operationalize and implement norms, and to examine how this varies across provider types and settings, is at the cutting edge of advances in the science of applied behavioral health economics. Research addressing both issues has the potential for high public health and scientific impact.

2.3.3 ASSESSMENT OF POTENTIAL RISKS AND BENEFITS

We believe that our study's significant potential benefits, especially in the current context of the opioid epidemic, far outweigh the minor and unlikely risks it may present to patients.

3 OBJECTIVES AND ENDPOINTS

OBJECTIVES	ENDPOINTS
Primary	
To test the effectiveness of two behavioral nudges, one based on peer behavior and one based on best practice guidelines, in reducing the share of discharge opioid prescriptions above procedure-specific prescribing guidelines	Share of discharge opioid prescriptions above prescribing guidelines
Secondary	
To test the effectiveness of two behavioral nudges, one based on peer behavior and one based on best practice guidelines, in reducing the morphine milligram equivalent quantities and days' supply prescribed at discharge	Morphine milligram equivalents (MMEs) prescribed at discharge, days' supply of opioids prescribed at discharge
To test the effectiveness of two behavioral nudges, one based on peer behavior and one	Share of discharges where any opioid was prescribed

OBJECTIVES	ENDPOINTS
based on best practice guidelines, in reducing the share of discharges with any opioids prescribed	
To test the long-term effects on patients of two behavioral nudges, one based on peer behavior and one based on best practice guidelines	Share of patients on opioids for greater than 3 months post-discharge
To test the persistence of the effectiveness of two behavioral nudges, one based on peer behavior and one based on best practice guidelines, in reducing the share of discharge opioid prescriptions above procedure-specific prescribing guidelines	Share of discharge opioid prescriptions above prescribing guidelines in the 12 months after the nudges stop being delivered
To test the safety of two behavioral nudges, one based on peer behavior and one based on best practice guidelines	Number of 30-day all-cause emergency department visits, number of 30-day all-cause hospitalizations

4 STUDY DESIGN

4.1 OVERALL DESIGN

We will conduct a three-arm cluster randomized controlled trial of two behavioral nudges compared to usual post-surgical care. One nudge will provide feedback on the surgeon's prescribing behavior relative to institutional prescribing guidelines (an injunctive norm); the other will provide feedback on their prescribing behavior relative to their peers (a descriptive norm). Three surgical specialties (general surgery, orthopedic surgery, and obstetric/gynecological surgery) within 19 hospitals will be randomized such that all surgeons within a given specialty at a given hospital will receive one of three conditions: control, guideline-based nudge, or peer-based nudge.

4.2 SCIENTIFIC RATIONALE FOR STUDY DESIGN

We chose a superiority design in order to make the strongest possible conclusions about whether our nudges are effective and support a policy recommendation as to whether healthcare systems should invest resources in implementing similar nudges.

In our control arm, surgeons will not receive any nudges and will not be informed of the study. By not informing them of the study, we will prevent a Hawthorne effect and obtain an accurate representation of status quo prescribing behavior against which to test the effects of the nudges.

4.3 JUSTIFICATION FOR DOSE

Using prescribing data from recent years at Sutter Health, we simulated how many surgeons would receive nudges and how many nudges they would receive under different study design parameters. From this we determined that delivering the nudges monthly achieved a balance between exposing them to the intervention and burdening them with emails. We chose to deliver the nudges by email because this method presents a low burden to surgeons, has been successful in a similar study conducted at Sutter Health,⁴⁵ and would be easily scalable beyond Sutter Health if our nudges prove effective.

4.4 END OF STUDY DEFINITION

The study is considered to be completed once data has been collected for one year after the date on which the final nudges were delivered.

5 STUDY POPULATION

5.1 INCLUSION CRITERIA

Eligible discharge prescriptions meet all of the following criteria:

- the patient is at least 18 years old at the date of surgery
- the patient is discharged to their home
- the surgical procedure has an applicable post-operative opioid prescribing guideline
- the surgical procedure is the only surgical procedure performed during the patient's hospital stay
- the prescription is for an opioid taken orally (tablets, capsules, or liquid solution)

5.2 EXCLUSION CRITERIA

To avoid contamination between the intervention arms, surgeons who operate across multiple surgical specialties (defined as surgeons who performed less than 90% of their total procedures in one specialty between 1 June 2020 and 31 May 2021) will not be eligible.

5.3 LIFESTYLE CONSIDERATIONS

Not applicable.

5.4 SCREEN FAILURES

Not applicable.

5.5 STRATEGIES FOR RECRUITMENT AND RETENTION

We will enroll surgeons by screening all surgeons present in electronic health record data from 1 June 2020 through 31 May 2021, and a waiver of informed consent has been granted by the RAND IRB, so surgeon-level recruitment is unnecessary. Hospitals have been recruited and will be retained through communication with hospital- and system-level administrators.

6 STUDY INTERVENTION

6.1 STUDY INTERVENTION(S) ADMINISTRATION

6.1.1 STUDY INTERVENTION DESCRIPTION

Surgeons randomized to our study intervention will receive one of two types of behavioral nudges delivered as monthly emails. The two nudges will be active for twelve months (October 2021–October 2022).

To ensure that the nudges target only *inappropriate* opioid prescribing, surgeons will receive nudges only when they write opioid prescriptions that exceed post-operative opioid prescribing guidelines developed by multidisciplinary teams at the Mayo Clinic.^{32, 46, 47} (and personal communication with [name], Ph.D., MPH, on opioid prescribing guidelines for caesarean section, March 12, 2021; unreferenced) These guidelines recommend ranges of 5mg oxycodone tablet quantities specific to the procedure performed and are partly based on patient surveys of actual post-operative opioid use.

In both nudge conditions, eligibility for receiving a monthly nudge is contingent upon at least two of the surgeon's patients being discharged with a post-operative opioid prescription exceeding the quantities specified by the Mayo Clinic guidelines. Though it may seem counterintuitive for the descriptive norm nudge to be based implicitly on prescribing guidelines, this choice ensures patient safety and avoids confounding the content of the nudge with the threshold for receiving a nudge.

Intervention arm 1: nudge based on descriptive norms

Surgeons randomized to this condition will receive an email with the following content at the end of each month in which at least two of their patients are discharged with a post-operative opioid prescription that exceeds the prescribing guideline for the procedure performed.

[Subject line: Your peers vs. your opioid prescribing safety record]

Dear Dr. [Name],

In an effort to reduce opioid use among our surgical patients, Sutter Health is reviewing opioid prescriptions and prescribing patterns for surgeons and will be communicating the findings.

In [month], at least **XX** of your patients were discharged with opioid prescriptions **exceeding** the amount prescribed by **YY%** of your peers for these procedures.

YY% of [specialty] surgeons at Sutter Health prescribe within the ranges below.

We will continue to send you opioid prescribing safety reports.

Sincerely,

[Signature(s) of chief medical executive, chief of staff, and/or surgical department chair at the surgeon's hospital]

[Table including each procedure type performed by this surgeon in the reference month and the corresponding "Amount prescribed by your peers (5mg oxycodone tablets)", with a footnote stating the conversion factors for hydrocodone and tramadol]

The ranges of 5mg oxycodone tablets displayed in the email will be the same as the ranges stipulated by the prescribing guidelines, but this nudge will not include any language about guidelines.

Intervention arm 2: nudge based on injunctive norms

This condition will be identical to the first condition, except the content of the monthly emails will refer to safety guidelines rather than the surgeon's peers.

[Subject line: Best practice guidelines vs. your opioid prescribing safety record]

Dear Dr. [Name],

In an effort to reduce opioid use among our surgical patients, Sutter Health is reviewing opioid prescriptions and prescribing patterns for surgeons and will be communicating the findings.

In [month], at least **XX** of your patients were discharged with opioid prescriptions **exceeding** the amounts recommended by safety guidelines for these procedures.

For patient safety, Sutter Health recommends prescribing within the ranges below for these procedures. Doing so will also meet best practice safety guidelines for post-operative opioid prescribing.

We will continue to send you opioid prescribing safety reports.

Sincerely,

[Signature(s) of chief medical executive, chief of staff, and/or surgical department chair at the surgeon's hospital]

[Table including each procedure type performed by this surgeon in the reference month and the corresponding "Amount recommended by Sutter Health (5mg oxycodone tablets)", with a footnote stating the conversion factors for hydrocodone and tramadol]

Control arm

Surgeons randomized to the control arm will not receive any nudges and will not be informed of the study. By not informing them of the study, we will prevent a Hawthorne effect and obtain an accurate representation of status quo prescribing behavior against which to test the effects of the nudges.

6.1.2 DOSING AND ADMINISTRATION

Nudges will be delivered monthly through the email software MyEmma.

6.2 PREPARATION/HANDLING/STORAGE/ACCOUNTABILITY

6.2.1 ACQUISITION AND ACCOUNTABILITY

Not applicable.

6.2.2 FORMULATION, APPEARANCE, PACKAGING, AND LABELING

Not applicable.

6.2.3 PRODUCT STORAGE AND STABILITY

Not applicable.

6.2.4 PREPARATION

The monthly nudges will be prepared by a project coordinator at Sutter Health using data extracted from Sutter Health's electronic health record by a data analyst at Sutter Health. They will be prepared by

filling in an email template designed and approved by all study investigators. Code used to produce the list of nudge recipients in each month and the information used to fill in the nudge email template (number of discharges with prescriptions above guidelines, procedures for which the receiving surgeon overprescribed, and percent of surgeons in the receiving surgeon's specialty who were compliant with guidelines) has undergone a quality assurance process in which two investigators independently developed code and compared results. The email software MyEmma will be used to prepare and send the nudges.

6.3 MEASURES TO MINIMIZE BIAS: RANDOMIZATION AND BLINDING

The study design has four levels: patients, surgeons, surgical specialties, and hospitals. Randomization will take place at the level of the surgical specialty, using a blocked scheme to ensure that each arm has a balance of large and small hospitals and a sample size of surgeons similar to the other two arms.

All investigators except the Sutter Health data analyst extracting the electronic health record data and the Sutter Health project coordinator preparing the nudges will be blinded to intervention assignment.

6.4 STUDY INTERVENTION COMPLIANCE

A project coordinator at Sutter Health will prepare and send the monthly nudges according to the predetermined schedule (sent on the third Tuesday each month from October 2021 through September 2022). This study team member will report to the site principal investigator, [name], and the study principal investigator, [name], after each nudge is sent.

6.5 CONCOMITANT THERAPY

Not applicable.

7 STUDY INTERVENTION DISCONTINUATION AND PARTICIPANT DISCONTINUATION/WITHDRAWAL

7.1 DISCONTINUATION OF STUDY INTERVENTION

The study's independent Data Safety Monitoring Board (DSMB) may make a recommendation to discontinue the study intervention at any time based on an assessment of the benefit/risk ratio of study participation. If the study intervention is discontinued, data will continue to be collected for another 12 months from the date of discontinuation.

7.2 PARTICIPANT DISCONTINUATION/WITHDRAWAL FROM THE STUDY

Participants may discontinue the study intervention at any time by contacting the investigators (an email address will be provided in each nudge) or by clicking the "Unsubscribe" button at the bottom of any nudge email. Their discontinuation and any reasons given will be recorded by the investigators. Data on their prescribing behavior will still be passively collected through the electronic health record until the study's data collection period ends.

7.3 LOST TO FOLLOW-UP

Not applicable.

8 STUDY ASSESSMENTS AND PROCEDURES

8.1 EFFICACY ASSESSMENTS

All efficacy assessments will be conducted using data collected from the Sutter Health electronic health record. Data collected will include:

- Unique study IDs of the patient, hospital location, procedural case record, hospitalization, opioid order, performing provider, discharging provider, and prescribing provider
- Patient sex, racial identity, ethnic identity, and age
- Patient tobacco use and chronic opioid use
- Patient diabetes, substance use disorder, mood disorder, and pain disorder diagnoses
- Patient BMI and ASA physical status rating
- Patient insurance status
- Procedure name, classification (Elective, Emergent, Return to OR, Urgent, Trauma), service line, date, start time, and completion time
- Hospital admission and discharge date and time
- Performing provider title, specialty, gender, medical school graduation year, and board certifications
- Discharge provider title, specialty, gender, medical school graduation year, and board certifications
- Prescribing provider title, specialty, gender, medical school graduation year, and board certifications
- Presence of any opioid prescriptions in the 30 days and 12 months prior to surgery
- Name, quantity, strength, route, date, and time of opioids prescribed in the 24 hours prior to discharge
- Discharge opioid prescription order date, start date, end date, discontinue date, generic name, brand name, strength, quantity, days' supply, class, and refills
- Non-opioid discharge prescription order date, start date, end date, discontinue date, generic name, brand name, strength, and quantity
- Dates and associated diagnoses of emergency department and inpatient visits within 30 days of discharge
- Discharge opioid prescription refills

8.2 SAFETY AND OTHER ASSESSMENTS

All safety assessments will be conducted using data collected from the Sutter Health electronic health record. Data collected will include:

- Dates and associated diagnoses of emergency department visits within 30 days of discharge
- Discharge opioid prescription refills

The study statistician will regularly create three reports for each outcome. Each report will feature a set of ratios indicating the relative frequency of adverse events in a different context. The reports will contain the numerator, denominator, and ratio, each individually reported. Reports will be produced at the end of each month of the trial, including through the 1-year post-intervention period. They will be presented and discussed at half-yearly DSMB meetings.

- Report 1: Adverse events per arm
 - a) Numerator: number of adverse events among intervention arm 1 (INT1) patients
 - Denominator: total number of INT1 patients meeting the inclusion criteria

- b) Numerator: number of adverse events among intervention arm 2 (INT2) patients
Denominator: total number of INT2 patients meeting the inclusion criteria
- c) Numerator: number of adverse events among the control patients
Denominator: total number of control patients meeting the inclusion criteria

- Report 2: Adverse events per arm among patients of surgeons who ever received a treatment email
 - a) Numerator: number of adverse events among patients whose surgeon ever received an INT1 email
Denominator: total number of patients whose surgeon ever received an INT1 email
 - b) Numerator: number of adverse events among patients whose surgeon ever received an INT2 email
Denominator: total number of patients whose surgeon ever received an INT2 email

Notes: Ever received an INT1/INT2 email means that the surgeon is included if they received an INT1/INT2 email in any month of the trial. We will also compare the report 2 ratios to the report 1 control ratio (item c above) for additional context.

- Report 3: Adverse events per arm among patients who were prescribed an opioid at discharge and whose surgeon who ever received a treatment email
 - a) Numerator: number of adverse events among patients prescribed opioids at discharge and whose surgeon ever received an INT1 email
Denominator: total number of patients prescribed opioids at discharge and whose surgeon ever received an INT1 email
 - b) Numerator: number of adverse events among patients prescribed opioids at discharge and whose surgeon ever received a nINT2 email
Denominator: total number of patients prescribed opioids at discharge and whose surgeon ever received an INT2 email
 - c) Numerator: number of adverse events among control patients prescribed opioids at discharge
Denominator: total number of control patients prescribed opioids at discharge

Notes: Ever received an INT1/INT2 email means that the surgeon is included if they received an INT1/INT2 email in any month of the trial.

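### Safety Reports 2 and 3 count patients discharged before their surgeon's first email as exposed, which shrinks any email-related excess risk in those two reports by the pre-email share

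*Combined protocol and SAP*

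**What the plan says.** Section 8.2 of the combined protocol and SAP plans three monthly safety reports for the DSMB.

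- **Report 1** compares whole arms. For intervention arm 1 the denominator is the "total number of INT1 patients meeting the inclusion criteria".
- **Report 2** narrows to surgeons who were emailed. Its arm 1 denominator is the "total number of patients whose surgeon ever received an INT1 email".
- **Report 3** adds an opioid prescription at discharge. Its arm 2 denominator is the "total number of patients prescribed opioids at discharge and whose surgeon ever received an INT2 email".

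The same note stands under Reports 2 and 3: "Ever received an INT1/INT2 email means that the surgeon is included if they received an INT1/INT2 email in any month of the trial". Neither report requires the discharge to follow the email, and section 9.4.3 only refers back to 8.2.

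The comparators carry no trigger condition. For Report 2 the plan says "We will also compare the report 2 ratios to the report 1 control ratio (item c above) for additional context". Report 3 uses the "total number of control patients prescribed opioids at discharge".

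On the trigger, section 6.1.1 says that "eligibility for receiving a monthly nudge is contingent upon at least two of the surgeon's patients being discharged" above the guideline quantity. Sections 1.3 and 6.4 place the emails on third Tuesdays from October 2021 to September 2022, and section 1.3 bases each on the previous calendar month. Section 8.2 does not say whether the monthly reports are cumulative or when counting starts.

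**The concern.** Exposure is fixed by an event that can come after the patient has left hospital. Once a surgeon receives one email, every trial patient of that surgeon can enter the exposed group, including those discharged months earlier, whose discharge prescription no email could have influenced.

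Report 1 already supplies the whole-arm view. What Reports 2 and 3 add is a focus on patients whose surgeons were actually nudged, and pre-email patients blur that focus. The DSMB sees these reports at its half-yearly meetings and may recommend discontinuing the intervention (section 7.1), so a diluted ratio in them could make a harm look smaller than it is.

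**Working it through.** The plan gives no event rate, trigger rate or threshold for these reports, so there is no figure to reproduce. The check has four steps.

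**1. Are pre-email patients necessarily included?** The triggering discharges come before the email they trigger. For a surgeon first emailed in December 2021 or later, the trigger month is November or later. At least two above-guideline discharges then fall inside the trial period but before the email, and Reports 2 and 3 have no rule that removes them. For a first email in November 2021 the trigger month is October, which straddles the likely start of counting.

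**2. Effect on the ratio.** Let f be the share of counted patients discharged before their surgeon's first email, and RR the true post-email rate ratio. With equal underlying risk before and after, and an email that acts through the discharge prescription:

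displayed RR = f × 1 + (1 − f) × RR = 1 + (1 − f)(RR − 1)

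**3. Size of f.** Inputs from the documents: the 12 email dates (19 October 2021 to 20 September 2022, from the third-Tuesday rule), and a baseline period ending 18 October 2021 (section 9.4.4). Assumptions: counting starts 19 October 2021, reports are cumulative, surgical volume is constant and equal across surgeons, and each surgeon triggers with a constant monthly probability q.

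f = Σ pₖdₖ / T, where pₖ is proportional to q(1 − q)^(k−1) over the waves sent by the report date, dₖ is the number of days from 19 October 2021 to wave k, and T is the number of days to the report date (163, 346 and 711 for the dates below).

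Example, q = 0.2 at 31 March 2022: six waves with d = 0, 28, 63, 91, 119, 147. The weights 0.2, 0.16, 0.128, 0.1024, 0.0819, 0.0655 sum to 0.738. The weighted mean is 41.24 / 0.738 = 55.9 days, and f = 55.9 / 163 = 34%.

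| q (assumed) | f, 31 Mar 2022 | f, 30 Sep 2022 | f, 30 Sep 2023 | True RR 1.20 displayed at 30 Sep 2022 |
|---|---|---|---|---|
| 0.8 | 4.5% | 2.1% | 1.0% | 1 + 0.979 × 0.20 = 1.20 |
| 0.2 | 34.3% | 27.1% | 13.2% | 1 + 0.729 × 0.20 = 1.15 |
| 0.05 | 43.1% | 42.7% | 20.8% | 1 + 0.573 × 0.20 = 1.11 |

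At q = 0.2 the displayed value is 1 + 0.657 × 0.20 = 1.13 at 31 March 2022 and 1 + 0.868 × 0.20 = 1.17 at 30 September 2023. If counting starts on 1 October 2021 instead, f at 30 September 2022 is 6.9%, 30.7% and 45.5% for the three values of q.

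For a single surgeon in a report at 30 September 2022, a first email in wave 1, 2, 4, 7 or 12 gives a pre-email share of 0%, 8%, 26%, 53% or 97%.

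**4. Surgeon selection.** If patients of ever-emailed surgeons have s times the baseline risk of all control patients, the displayed ratio is s × [1 + (1 − f)(RR − 1)]. With RR = 1.20 and f = 0.27 the bracket is 1.146. At s = 0.8 the display is 0.8 × 1.146 = 0.92, and at s = 1.2 it is 1.2 × 1.146 = 1.38. Both values of s are assumptions.

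**The case against.** Much can be said for the plan.

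- **Other safety information is untouched.** A reader might infer that any harm signal reaching the DSMB is diluted. The documents do not support that. Report 1 compares randomised arms without the email rule and goes to the same board. Thirty-day emergency visits and hospitalisations are also secondary outcomes in the hierarchical model (9.4.2) on the intention-to-treat dataset (9.3), and serious events are reported individually (8.3.6). No test or threshold hangs on Reports 2 and 3, and Report 2's comparison with control is offered only as context. This stands and limits the point to two supplementary reports.
- **The direction is not settled.** A reader might also infer that the displayed comparisons are biased towards no harm. Step 4 shows that selection of surgeons can outweigh the dilution either way. This stands.
- **Pre-email months are not simply low-prescribing months.** It is tempting to say that they all fall below the trigger. The month that triggers the first email has at least two above-guideline discharges by definition and precedes the email. Only earlier trial months fall below two.
- **Retroactive change is not documented.** Patients move into past figures only if reports are cumulative. If each report covers one month's discharges and emails to date, only the month of first email is affected.
- **The size may be small.** If most surgeons are first emailed in October 2021, f is near zero. The reports pool patients, so surgeons count by volume. If busy surgeons trigger sooner, the pooled f lies below the equal-volume figures above.
- **The DSMB charter may define the data elements** (10.1.6). It is not among the documents, and nothing in them corrects the rule in 8.2.

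None of this supplies a rule that the discharge must follow the email.

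**Conclusion.** The point holds for Reports 2 and 3 only. As written, both count patients discharged before their surgeon's first email as exposed, and no other section corrects this. The mechanism is certain and its size is not: across the assumed trigger probabilities, between about 2% and 43% of any email-related excess risk is lost in a cumulative report at 30 September 2022. With q = 0.2 the loss is larger around the first half-yearly review and about half as large a year after the last emails. These figures depend on cumulative counting, the start date, equal volumes and a constant q, none of which the documents give. The formula describes the dilution alone, and the net bias against all controls has no fixed sign. Because the reports exist to isolate nudged surgeons, and the correction is cheap, the change should be made.

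**What to change.** 1. Keep Report 1 as the main safety comparison.
2. In the notes to Reports 2 and 3, replace the exposure definition with: patients are counted from the date of their surgeon's first INT1 or INT2 email; earlier discharges of the same surgeons appear in a separate pre-email row; a patient's row is fixed at discharge.
3. Add a control row to both reports: patients of control surgeons discharged on or after the date an email would first have been sent under the same trigger. Dating only the email arms would leave the selection mismatch and add a calendar-time mismatch. Before a surgeon's first email nothing has been sent to that surgeon, so the first trigger arises in the same way in every arm, apart from spillover among colleagues. Report 3 also conditions on an opioid at discharge, which the emails may change, so it stays descriptive.
4. State whether the monthly reports are cumulative and on what date counting starts.

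The data are to hand: discharge date and time are collected (8.1), the email schedule is fixed and each sending is reported (6.4), and the recipient-list code already applies the trigger. The cost is slightly smaller denominators and a few more lines of report code.
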